7.5.2 Secondary Efficacy Analyses

PFS rate at 2 years and the corresponding two-sided 95% CI for each treatment arm, along with the one-sided 95% CI for the difference of PFS rate at 2 years between the treatment arms will also be calculated using the same method for PFS rate at 6 months described in the primary efficacy analysis.

OS will be summarized by KM product-limit method for all randomized patients. Median values of OS, along with two-sided 95% CI will be calculated for each treatment arm using the same method as for PFS. The hazard ratios between treatment arms along with the 95% CI will also be produced from a stratified Cox proportional hazard model as for PFS. Survival rates at 6, 12, 18, 24, and 36 months will be estimated for each treatment arm. Minimum follow-up must be longer than time point to generate the rate. The two-sided 95% CIs for OS rates at each time point for each treatment arm, along with the one-sided 95% CI for the difference of OS rates at each time point between two treatment arms will be calculated using the same method for PFS rates. OS rates at each time point and corresponding two-sided 95% CI for each treatment arm, along with the one-sided 95% CI for the difference of OS rates at each time point between the treatment arms will also be calculated adjusting for stratifying factors - tumor histology and response criteria using the inverse variance weight as for PFS rates.

The status of subjects who are censored in the OS Kaplan-Meier analysis will be tabulated for each treatment arm using following categories:

- on-study (on-treatment and not progressed, on-treatment progressed, in follow-up);
- off-study: (lost to follow-up, withdraw consent, etc.).

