**Figure 3.1-1: Study Design Schematic**

Each subject’s last study visit will be defined as the last on-treatment or follow-up visit that occurs prior to the date of 3 years after the initiation of randomized therapy. The study will be completed no later than 3 years after the last subject’s first visit.

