### **3.6 Post Study Drug Study Follow up**

In this study, PFS is a key endpoint of the study. Post-study follow-up is of critical importance and is essential to preserving subject safety and the integrity of the study. Subjects who discontinue study drug must continue to be followed for collection of outcome and/or survival follow-up data as required and in line with Section 5 until death or the conclusion of the study.

BMS may request that survival data be collected on all treated/randomized subjects outside of the protocol-defined window in [Table 5.1-3](#). At the time of this request, each subject will be contacted to determine their survival status unless the subject has withdrawn consent for all contacts or is lost to follow-up.

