2.1 Study Design

This is an open-label, randomized phase IIIb/IV dose frequency optimization trial in adult patients with advanced/metastatic (Stage IIIb/IV) NSCLC (non-Sq and Sq). Subjects will have received approximately up to 12 months (52 weeks) of nivolumab therapy at either 3 mg/kg or 240 mg every 2 weeks and achieved a complete response (CR), partial response (PR), or stable disease (SD) as evidenced by 2 consecutive tumor assessments prior to enrollment. At enrollment, subjects will be randomized 1:1 to receive either 240 mg every 2 weeks (Arm 1) or 480 mg every 4 weeks (Arm 2). Randomization will be stratified by histology (Sq vs. Non-Sq) and response criteria to pre-study nivolumab at randomization (CR or PR vs. SD). For subjects receiving nivolumab 240 mg every 2 weeks, each 14-day dosing period will constitute a cycle. For subjects receiving nivolumab 480 mg every 4 weeks, each 28-day dosing period will constitute a cycle.

Subjects will continue treatment until disease progression or unacceptable toxicity for a maximum of 2 years from first randomized dose. The follow-up period begins when the decision to permanently discontinue a subject from study therapy is made (no further treatment or retreatment with nivolumab is anticipated). All subjects who discontinue study drug should comply with protocol specified follow-up procedures as outlined in Section 5 of the Clinical Protocol until death or the conclusion of the study. The only exception to this requirement is when a subject withdraws consent for all study procedures including post-treatment study follow-up or loses the ability to consent freely.

The study design schematic is presented in [Figure 2.1-1](#).

Figure 2.1-1: Study Schema

Each patient’s last study visit will be defined as the last on-treatment or follow-up visit that occurs prior to the date of 3 years after the initiation of randomized therapy. The study will be completed no later than 3 years after the last subject’s first visit.

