2.5 Data Monitoring Committee

A Data Monitoring Committee (DMC) will be established to provide oversight of safety and efficacy (including assessment of 6 month PFS co-primary endpoint) considerations and to provide advice regarding actions the committee deems necessary for the continuing protection of enrolled patients and those yet to be recruited to the trial as well as for the continuing validity and scientific merit of the study results. The DMC is charged with assessing such actions in light of an acceptable benefit/risk profile for nivolumab.

One safety interim review will be conducted after 25 patients per treatment arm reach at least 3 months of treatment exposure after randomization. The DMC will review all available safety data and any available efficacy data that is provided. These efficacy data will be provided to allow evaluation of safety in the context of benefit. One formal interim review will be conducted at minimum of 6 months after the last patient's first visit. The DMC will review the analysis for 6-month PFS and OS as well as the safety data. In addition, it is anticipated that the DMC will meet at every 12 months or more frequently if deemed necessary for the duration of the trial to perform safety assessments.

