4.2 Secondary Endpoints

- PFS rate at 1 year after randomization by tumor histology (Sq vs. Non-Sq) and RECIST v1.1 response (CR or PR vs. SD) assessed before randomization
- PFS rate at 2 years after randomization
- OS rate at 1 year and OS rate up to 3 years after randomization by arm, tumor histology, and RECIST v1.1 response status at randomization (CR or PR vs. SD). OS is defined as time from the date of randomization to the date of death. Patients who did not die by the end of the study will be censored at the last known date alive. OS rate at 1 year is the rate from Kaplan-Meier estimated at one year after randomization.
- Safety and tolerability of nivolumab, as measured by incidence and severity of AEs and specific laboratory abnormalities.

Safety endpoints include adverse events (AEs), serious adverse events (SAEs), AEs leading to discontinuation, AEs leading to dose delay, immune-mediated adverse events (IMAEs), select adverse events (select AEs), other events of special interest, and deaths. Adverse events will be coded and grouped into Preferred Terms (PT) by System Organ Class (SOC), using the most current version of Medical Dictionary for Regulatory Activities (MedDRA). The intensity of AEs will be graded 1 to 5 according to the National Cancer Institute Common Terminology Criteria for Adverse Events (CTCAE) Version 4.0. The use of immune modulating concomitant medication will be also summarized. In addition specific clinical laboratory tests and vital signs will be analyzed.

[REDACTED]

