8 CONVENTIONS

The following conventions may be used for imputing partial dates for analyses requiring dates:

- For missing and partial AE onset dates, imputation will be performed using the Adverse Event Domain Requirements Specification.
- For missing and partial AE resolution dates, imputation will be performed as follows:
 - If only the day of the month is missing, the last day of the month will be used to replace the missing day
 - If the day and month are missing or a date is completely missing, it will be considered as missing.
- Missing and partial non-study medication domain dates will be imputed using the derivation algorithm described in Section 4.3.3 of BMS Non-Study Medication Domain Requirements Specification.

For death dates, the following conventions will be used for imputing partial dates:

- If only the day of the month is missing, the 1st of the month will be used to replace the missing day. The imputed date will be compared to the last known date alive + 1 day and the maximum will be considered as the death date.
- If the month or the year is missing, the death date will be imputed as the last known date alive + 1 day.
- If the date is completely missing but the reason for death is present the death date will be imputed as the last known date alive + 1 day

For the date of progression, the following conventions will be used for imputing partial dates:

- If only the day of the month is missing, the 1st of the month will be used to replace the missing day*.
- If the day and month are missing or a date is completely missing, it will be considered as missing.

* In the case of the date of death being present and complete, the imputed progression date will be compared to the date of death. The minimum of the imputed progression date and date of death will be considered as the date of progression.

For other partial/missing dates, the following conventions will be used:

- If only the day of the month is missing, the 15th of the month will be used to replace the missing day.
- If both the day and the month are missing, “July 1” will be used to replace the missing information.
- If a date is completely missing, it will be considered as missing.

The following conversion factors will be used to convert days to months or years: 1 month = 30.4375 days and 1 year = 365.25 days.

Duration (e.g. time from first diagnosis of NSCLC to randomization, time-to onset, time-to resolution) will be calculated as follows:

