Duration = (Last date - first date + 1)

Last known date alive will be defined based on all appropriate dates collected on the CRF.

All statistical analyses will be carried out using SAS (Statistical Analysis System software, SAS Institute, North Carolina, USA) unless otherwise noted.

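### The 36-month OS rate requires follow-up strictly longer than 36 months, but the study closes no later than 3 years after the last subject's first visit and no survival contact is required at month 36

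*SAP*

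**What the plan says.** - **Endpoint.** SAP 4.2 lists as secondary "OS rate at 1 year and OS rate up to 3 years after randomization by arm". OS runs from randomization.
- **Condition.** SAP 7.5.2: "Survival rates at 6, 12, 18, 24, and 36 months will be estimated for each treatment arm. Minimum follow-up must be longer than time point" for a rate to be generated. SAP 7.5.1 applies the same condition to PFS rates. SAP 7.5.3 plans 36-month OS rates with bootstrap intervals and does not restate the condition. SAP 7.5.5 repeats the 36-month milestone by subgroup, by the method of the primary analysis.
- **Study end.** SAP 2.1, and Protocol 3.1 in the same terms: "The study will be completed no later than 3 years after the last" subject's first visit.
- **Each subject's last visit.** Protocol 3.1 (below Figure 3.1-1), matched by SAP 2.1: the "last on-treatment or follow-up visit that occurs prior to the date of 3 years after the initiation of randomized therapy".
- **After stopping drug.** Protocol 3.6 requires collection of outcome and/or "survival follow-up data as required and in line with Section 5 until death or the conclusion of the study". It also lets the sponsor request survival data outside the scheduled window. Protocol Table 5.1-3 sets survival contacts every 6 months (±1 month) after Follow-Up Visit 2 for up to 3 years, accepts phone or e-mail, and in the text shown does not say from when the 3 years run.
- **Day counting.** SAP 8: "1 month = 30.4375 days and 1 year = 365.25 days", and "Duration = (Last date - first date + 1" day).
- **A related anchor.** SAP 2.5: "One formal interim review will be conducted at minimum of 6 months after the last" patient's first visit.

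**The concern.** A strict inequality is set against a maximum of the same nominal length. Read literally, whether the 36-month rate may be reported depends on two undefined terms and on a day or so of calendar arithmetic. Month 36 is the only SAP milestone beyond 24 months for an endpoint described as running to 3 years. The trial is open-label, so these definitions should not be settled after the data have been seen.

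Reporting the rate does not remove the problem. The number documented at risk at month 36 then depends on which follow-up passage sites applied and on whether the optional survival sweep was done.

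**Working it through.** **1. The plan's own lengths.** 36 × 30.4375 = 1095.75 days and 3 × 365.25 = 1095.75 days, so the study limit is exactly 36.000 months. The condition needs more than 36.

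**2. Last subject's follow-up from randomization at the latest permitted study end.** A calendar 3-year span is 1095 or 1096 days. Days available = (first visit minus randomization) + 1095 to 1096. The 28-day lag is an assumption taken from the screening-scan window in Protocol Table 5.1-1; the 3- and 7-day gaps are also assumed.

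| First visit is | Days from randomization | Months | Against 1095.75 days |
|---|---|---|---|
| Screening, 28 days earlier | 1067 to 1068 | 35.06 to 35.09 | -28.75 to -27.75 |
| Randomization | 1095 to 1096 | 35.98 to 36.01 | -0.75 to +0.25 |
| First dose, 3 days later | 1098 to 1099 | 36.07 to 36.11 | +2.25 to +3.25 |
| First dose, 7 days later | 1102 to 1103 | 36.21 to 36.24 | +6.25 to +7.25 |

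The SAP 8 duration rule adds one day to each row, so the randomization row becomes +0.25 to +1.25. If minimum follow-up is instead counted from the last subject's first visit, as SAP 2.5 does for the 6-month review, the two clocks start together and the randomization row applies whatever first visit means. The span is 1096 days when it contains a 29 February. That holds for any first visit from 1 March 2017 to 26 June 2018, the date of Revised Protocol 05; the documents do not give the last subject's date.

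**3. Scheduled contacts for a subject treated for 2 years.** Take the last dose at months 23.0 to 24.0. Follow-Up Visit 1 is at 30 ± 5 days and Visit 2 is 70 ± 5 days later, so Visit 2 falls 90 to 110 days after last dose, at months 26.0 to 27.6. The next contact (+6 ± 1 months) is at 31.0 to 34.6. The one after (+12 ± 1 months, measured from Visit 2) is at 37.0 to 40.6, past the cap. No scheduled contact falls at month 36.

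**4. Illustration of precision.** Not from the documents: OS of 0.50 at month 36, exponential survival, treatment stop uniform over 0.5 to 24 months, accrual of 12 to 31.7 months. From the documents: 350 subjects, so 175 per arm. The optional sweep is excluded. Simulated results per arm:

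- *Cap with scheduled contacts only:* about 0, 1.4 and 3.4 documented at risk for randomization-to-dose gaps of 0, 3 and 7 days. Hand check: 175 × 0.50 = 87.5 survivors; 3/182.6 × 87.5 = 1.4 and 7/182.6 × 87.5 = 3.4. SD of the month-36 estimate is 0.047 to 0.058.
- *Followed to study conclusion:* 65 to 79 at risk, SD about 0.038.
- *Contact required at month 36:* about 88 at risk. Hand check of the SD: √(0.50 × 0.50/175) = 0.038.

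The mean Kaplan-Meier value is about 0.50 in all three. One-sided 95% margin for the arm difference = 1.645 × √2 × SD: 0.047 gives 0.109, 0.058 gives 0.135, 0.038 gives 0.088.

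**The case against.** The best defence has five parts.

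- **Day count.** With the SAP 8 rule the condition passes by 0.25 to 1.25 days when first visit is randomization. SAP 2.5 times the 6-month PFS review from the last patient's first visit, which fits a first visit near randomization better than one at screening. This stands as a possible reading. But SAP 8 does not name minimum follow-up among its durations, and the pass needs the study to run to its last permitted day or the day before.
- **Section 7.5.3.** A sensitivity analysis may be taken to inherit the condition on the analysis it supports. That is fair: silence there is not a waiver. It leaves the matter unclear, which one sentence would cure.
- **Visits are not contacts.** The 3-year cap concerns visits, while survival status can be collected by phone or e-mail, and the sponsor may sweep all subjects. The means therefore exists. It is optional and undated, and it does not move the study end.
- **Missing schematic.** The study figures are not shown and may state the origin of the 3-year follow-up. The remark on Table 5.1-3 is therefore limited to the text available.
- **Small consequence.** The comparison is descriptive and secondary, and the OS curve, median and hazard ratio carry no such condition. This stands and limits the weight of the point.

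**Conclusion.** The conflict is in the text. Applied literally, the plan either withholds its 36-month OS rate or lets it hang on days, according to definitions it does not give. The arithmetic in steps 1 to 3 needs only the documents plus the stated lags. The precision figures (11 to 13 points against 9) are illustrative: they rest on assumed survival, stop times and randomization-to-dose gaps and on leaving out the optional sweep. With no gap, the month-36 value is merely the curve carried forward.

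A reader might infer more than this:

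- *That the 36-month rate can never be reported, or that any study end before the last permitted day rules it out.* Not so. A first visit at first dose, after randomization, leaves a few days of slack.
- *That 7.5.3 definitely reports what 7.5.2 withholds.* The SAP does not say either way.
- *That 7.5.5 drops the condition.* It appears to inherit it by pointing to the primary-analysis method.
- *That the OS estimate is biased.* Bias is not inherent if deaths and survivors are ascertained to the same date; the expected cost is precision.

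Co-primary PFS, OS rates through 24 months, and the OS curve, median and hazard ratio are unaffected. It is worth correcting before the OS cutoff, because contacts missed at month 36 may not be fully recoverable.

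**What to change.** 1. **SAP 7.5.2.** Define minimum follow-up as the time from the last subject's randomization to the OS data cutoff, name the day count used, and require it to be at least the time point. Ascertain deaths and survivors to that same cutoff. State that the rule also governs 7.5.3, and confirm it for 7.5.5.
2. **Protocol 3.1, 3.6 and Table 5.1-3, and SAP 2.1.** Define first visit and reconcile the follow-up passages for survival status, giving the 3 years in the table an origin.
3. **Month-36 sweep.** Schedule the already permitted phone or e-mail contact for every subject not known to be dead, at or just after 36 months (day 1096 or later) from randomization.
4. **If the study-end rule prevents this for the last subjects**, for example because first visit is screening, either let the survival contact fall after the 3-year date, or restate the last OS milestone in SAP 7.5.2, 7.5.3 and 7.5.5 and the secondary endpoint to one that follow-up supports; 24 months is the next one already listed. Extending the study is an option, not a requirement.

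The cost is one remote contact per subject not known to be dead and possibly a cutoff a few weeks later. A change to follow-up or study end is a protocol revision needing ethics approval under Protocol 9.1.1. If the milestone is restated instead, the cost is wording only, at the price of giving up the 36-month rate.

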7.5.3 Sensitivity Analysis

The following sensitivity analysis will be conducted:

- Same analyses for PFS described in [Section 7.5.1](#) will be repeated for per-protocol subjects
- The PFS rate at 6 months and 12 months will be calculated using KM estimates on the PFS curve for each randomized treatment arm. The two-sided unadjusted 95% CI for PFS rates at 6 months and 12 months for each treatment arm and the one-sided unadjusted 95% CI for the difference of PFS rates between two treatment arms will be calculated.
- For the 6-month analysis, the 99.3% one-sided unadjusted CI around the difference in PFS rates between two treatment arms will be generated. A 95.2% one-sided unadjusted CI around the difference in PFS rates at 12 months will also be generated. With the significant reduction of sample size due to the early stop of enrolment of the study, the adjustment of alpha between 6 months and 12 months PFS rates will not be conducted. Instead, 95% one-sided unadjusted confidence interval around the difference of PFS rates will be generated.
- OS rates at 36 months for each treatment arm and the difference of OS rates at each time point between two treatment arms will be estimated using KM method. The two-sided 95% CI for OS rates at each time point for each treatment arm and the one-sided 95% CI for the difference of OS rates at each time point between two treatment arms will be calculated using bootstrapping estimation method. Compute the Kaplan-Meier estimator for the bootstrap sample, $\hat{S}_X^*(t)$. Take 10000 bootstrap samples, and compute the Kaplan-Meier estimators for each bootstrap sample at the time point t. To be specific, let $\hat{S}_X^{*1}, \hat{S}_X^{*2}, \dots, \hat{S}_X^{*10000}$ be the corresponding estimations at time point t of the bootstrap samples. For two-sided 95% CI of OS rates within each treatment arm, sort the estimates in ascending order and select the values that cut off the lower and upper 2.5 percentiles to give lower and upper limit of 95% CI.
For the difference of OS rates at time t between two treatment arms, let $\hat{S}_E^{*1} - \hat{S}_C^{*1}, \hat{S}_E^{*10000} - \hat{S}_C^{*10000}$ be the difference of OS rates between Arm 2 and Arm 1 for bootstrap sample 1, sample 10000. For one-sided 95% CI for the difference of OS rates between two treatment arms, sort the estimates in ascending order and select the value that cut off the lower 5 percentiles to give lower limit of 95% CI.
- Extent of follow-up for OS will be summarized for each treatment arm. Extent of follow-up will be assessed by the duration between randomization date and death date or last known date alive for subjects who are still alive.

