7.5 Efficacy

7.5.1 Primary Efficacy Analysis

The coprimary objectives will be assessed by PFS rate at 6 months and PFS rate at 12 months. PFS will be summarized by Kaplan-Meier product-limit method for all randomized patients. Median values of PFS, along with two-sided 95% CI using Brookmeyer and Crowley method (a log-log transformed CI for the survivor function $S(t)^{2,3}$, will be calculated for each treatment arm.

The hazard ratios between treatment arms along with the one-sided 95% CI will be produced from a stratified Cox proportional hazard model (by tumour histology [Sq vs. Non-Sq] and response category at randomization [CR or PR vs. SD]).

PFS rates at 6 months and 12 months will be calculated using KM estimates on the PFS curve for each randomized treatment arm. Minimum follow-up must be longer than the time point to generate the rate. The two-sided 95% CIs, adjusted for stratifying factors (by tumor histology (Sq vs. Non-Sq), response criteria (CR or PR vs. SD) using inverse variance weight, for PFS rates at 6 months and 12 months will be calculated for each treatment arm, along with one-sided 95% CI for the difference between the two treatment arms using the Greenwood formula⁴ for variance derivation. Denote $\hat{S}_i(t)$ as an estimate of survival function from Kaplan-Meier estimate and

$\hat{Var}(S_i(t))$ as the variance of estimation for stratum i at time t, respectively, w_i as the weight for

stratum i, defined as
$$\frac{1/\hat{Var}(\hat{S}_i(t))}{\sum_{i=1}^k [1/\hat{Var}(\hat{S}_i(t))]}$$
 where k is the number of strata (k = 4). Then the weighted

survival estimate for PFS rate across all the strata at time t is
$$\sum_{i=1}^k w_i \hat{S}_i(t)$$
 and weighted variance of

estimation is
$$\hat{\sigma}_w^2 = \frac{1}{\sum_{i=1}^k 1/\hat{Var}(\hat{S}_i(t))}$$
. The two-sided 95% CIs for the PFS rates for each treatment

arm will be calculated as
$$\sum_{i=1}^k w_i \hat{S}_i(t) \pm z_{(1-\alpha/2)} \times \hat{\sigma}_w$$
, where $\alpha=0.05$.

The estimated PFS rate difference at time t between two treatment arms is
$$\hat{S}_{E_i}(t) - \hat{S}_{C_i}(t)$$
, where

$\hat{S}_{E_i}(t)$ is the estimated PFS rate for 480 mg every 4 weeks treatment arm (Arm2) for stratum i

and $\hat{S}_{C_i}(t)$ is the estimated PFS rate for 240 mg every 2 weeks treatment arm (Arm 1) for stratum i. The variance for PFS rate difference between two treatment arms at time t for stratum i

is
$$\hat{Var}(\hat{S}_{E_i}(t)) + \hat{Var}(\hat{S}_{C_i}(t))$$

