APPENDIX 1 SELECT ADVERSE EVENTS DEFINITION AND CONVENTIONS

The select Adverse Events (select AEs) consist of a list of preferred terms grouped by specific category (e.g. pulmonary events, gastrointestinal events categories) and by subcategory (e.g. thyroid disorders, diabetes, pituitary, adrenal disorders subcategories). These categories and subcategories are defined by the Sponsor and the list that is most current at the time of analysis will be used. Also changes may be made to this list with each new version of MedDRA.

For information, the select AEs defined at the time of finalization of the first version of the document are listed in [Table 11-2](#) using MedDRA version 16. The updated list of select AEs will be used at the time of analysis and the final list used for the clinical study report will be included in an Appendix of the CSR.

Time-to onset definition

Time-to onset of select AE (any grade) for a specific category (i.e. pulmonary events, gastrointestinal events, ...) is defined as the time between the day of the first dose of study treatment and the onset date of the earliest select AE (of any grade) in this category.

If the subject did not experience a select AE (of any grade) in the category, time-to onset will be censored at the maximum follow-up time for all subjects in their respective treatment group (i.e. for subjects without an event, follow-up time is defined from first dosing date up to last dosing date + 30 days (or 100 days depending on the analysis), otherwise it is defined up to the last known alive date). The resulting Kaplan-Meier plot will present the cumulative rate of the select AE (any grade) in the category over time.

Time-to onset of select AE (grade 3-5) for a specific category is defined similarly but restricted to grade 3-5 select AEs.

Time-to onset of drug-related (grade 3-5 or any grade) select AE for a specific category is defined similarly but restricted to drug-related select AEs.

Time-to onset for a specific subcategory is defined similarly but restricted to event of this subcategory.

Time-to resolution definition

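### The by-arm summary of OS follow-up stops the clock at death, so it reflects mortality as well as how long subjects were observed

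*SAP*

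**What the plan says.** In SAP 7.5.3 (Sensitivity Analysis), "Extent of follow-up for OS will be summarized for each treatment arm", and it is "assessed by the duration between randomization date and death date or last known date alive for subjects who are still alive". SAP 4.2 defines OS from randomization to death, with survivors censored at the last known date alive. The two durations are therefore the same quantity.

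Separately, SAP 7.5.1 attaches a condition to the PFS milestone rates: "Minimum follow-up must be longer than the time point to generate the rate". SAP 7.5.2 repeats it for OS ("Minimum follow-up must be longer than time point to generate the rate"), where "Survival rates at 6, 12, 18, 24, and 36 months will be estimated for each treatment arm". The 2-year PFS rate picks up the condition by reference, since it "will also be calculated using the same method for PFS rate at 6 months described in the primary efficacy analysis". Neither section defines minimum follow-up, and neither refers to 7.5.3.

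**The concern.** Readers use a follow-up table to judge how mature the data are and whether the two arms were observed equally. A measure that ends at death cannot separate a subject who was lost at 10 months from one who was fully observed and died at 10 months. If survival differs between arms, the table will show an imbalance in follow-up that did not occur. If survival is poor in both arms, it will understate maturity in both.

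This matters somewhat more here than usual. The sample size was cut to about 350 and the formal non-inferiority test was dropped, so readers will weigh the estimates and their maturity directly. The trial is also open-label, which makes evidence of equal observation in the two arms more important.

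**Working it through.** The plan states no follow-up figure, so there is none to reproduce. The check asks what the SAP's definition returns when true observation time is known.

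**Inputs.** From the documents: the follow-up definition (SAP 7.5.3), the OS definition (SAP 4.2), and the statistics used for continuous variables, which include mean and median (SAP 7.1). Assumed: exponential OS, no loss to follow-up, 36 months of potential follow-up for every subject, 12-month OS (S12) of 0.70, 0.75 or 0.80, and a death hazard ratio of 1.3 between arms.

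**Step 1: closed form.** The hazard is λ = −ln(S12)/12. The SAP median is min(36, ln 2/λ) in one arm and min(36, ln 2/(1.3λ)) in the other. For S12 = 0.75, λ = 0.28768/12 = 0.02397, so ln 2/λ = 28.9 and ln 2/(1.3λ) = 22.2.

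| Assumed S12 | SAP median, reference arm | SAP median, hazard ratio 1.3 | Apparent gap | True gap |
|---|---|---|---|---|
| 0.70 | 23.3 | 17.9 | 5.4 | 0 |
| 0.75 | 28.9 | 22.2 | 6.7 | 0 |
| 0.80 | 36.0 | 28.7 | 7.3 | 0 |

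The mean moves less. It equals (1 − e^(−36λ))/λ. At S12 = 0.75 this is (1 − 0.4219)/0.02397 = 24.1 months, against (1 − 0.3256)/0.03117 = 21.6 months, a gap of 2.5 months.

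**Step 2: staggered entry.** Simulation with uniform accrual over 24 months, administrative censoring only, and 20,000 subjects per scenario:

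| Assumed S12 | SAP median, cut-off 12 months after last entry | Reverse KM | SAP median, cut-off 36 months after last entry | Reverse KM |
|---|---|---|---|---|
| 0.90 | 21.5 | 24.0 | 42.5 | 47.8 |
| 0.80 | 19.0 | 24.2 | 36.3 | 47.8 |
| 0.70 | 16.4 | 24.0 | 23.4 | 48.0 |
| 0.60 | 14.1 | 24.0 | 16.4 | 48.0 |

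Within each cut-off, potential follow-up is the same in every row. The SAP median falls as mortality rises. Reverse Kaplan-Meier recovers the potential follow-up of about 24 or 48 months each time.

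**Step 3: where the distortion does not show.** If fewer than half of each arm die within a common 36 months, both medians sit at 36. In the same simulation with all subjects entering together, S12 of 0.90 and of 0.80 both gave 36.0. The median is then uninformative rather than misleading, though the mean still depends on deaths.

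**Step 4: the condition on milestone rates, texts side by side.** SAP 2.5 times the review of 6-month PFS from the last patient: "One formal interim review will be conducted at minimum of 6 months after the last patient's first visit". Protocol 1.5 uses minimum follow-up, in describing another study, for how long that study had been followed. The Revised Protocol 05 summary of changes uses a minimum for planned OS follow-up. All three fit a study-level meaning, such as last subject's randomization to cut-off. On that meaning, deaths have no effect on whether a rate may be produced. One difficulty remains. SAP 2.1 ends the study no later than 3 years after the last subject's first visit, so follow-up strictly longer than 36 months cannot be reached for the last subject, yet SAP 7.5.2 plans a 36-month OS rate.

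**The case against.** The strongest reply is that this is a descriptive line whose formula is stated openly. It enters no Kaplan-Meier estimate, variance, weight or interval. The SAP also tabulates the status of censored subjects by arm for PFS and OS, including loss to follow-up and withdrawal, so a careful reader has other evidence on completeness. The figures rest on assumed survival, and the trial's hypothesis is that the arms are similar. At a cut-off nearer the co-primary analysis the gap is smaller: 19.0 against 16.4 months for 12-month OS of 0.80 and 0.70. That is 2.6 months at a hazard ratio of ln 0.70/ln 0.80 = 1.6.

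Most of this stands and limits the point to reporting. It does not rescue the measure. Censoring tables give counts and reasons, not length of observation, and a summary that moves with mortality answers a different question from the one its label poses.

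A reader might go further and carry the 7.5.3 definition into the minimum follow-up condition. One death before 6 months would then block every rate, including the co-primary ones. With 350 subjects and 99% surviving to the time point, the chance of no death is 0.99^350 = 3%. The documents do not support that reading. Sections 7.5.1 and 7.5.2 never point to 7.5.3, the wording they use differs, 7.5.3 is confined to OS, and the texts in step 4 favour a study-level meaning. Nor is 7.5.3 the SAP's only definition of follow-up: in Appendix 1, for adverse-event onset, "follow-up time is defined from first dosing date up to last dosing date + 30 days" (or 100 days), otherwise up to the last known alive date.

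**Conclusion.** The concern holds for the follow-up summary. As defined, it is OS time without the event indicator, and under equal observation it makes the arm with more deaths look less followed. In the central example (12-month OS 0.75, hazard ratio 1.3, 36 months potential for all), the medians are 28.9 and 22.2 months where both should be 36. The direction follows from the definition. The size rests on assumed survival, accrual and cut-off: it shrinks at earlier cut-offs and in the mean, and the median gap vanishes if both medians reach the ceiling.

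No PFS or OS rate, difference or confidence interval is affected. The condition on milestone rates is not shown to fail. It is an undefined term that needs a clarifying sentence, together with a mismatch between a strict inequality, the 36-month OS rate and the 3-year study end.

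**What to change.** In SAP 7.5.3, replace the definition: report follow-up by arm with reverse Kaplan-Meier (deaths censored at the date of death, survivors counted as events at the last known date alive), and add the range of time from randomization to clinical cut-off.

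As a minor clarification in SAP 7.5.1 and 7.5.2, state that minimum follow-up means the time from the last subject's randomization to the clinical cut-off. Do not keep the strict inequality unchanged, because with this definition it would rule out the planned 36-month OS rate. Changing it to at least would be enough only if the last subject's first visit in SAP 2.1 coincides with randomization. If that visit is screening, randomization comes later and the 36-month rate needs an explicit exception or a reworded condition.

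The cost is a few sentences in the SAP and a line of code that reverses the censoring indicator. No new data are needed.
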